9. INTERIM ANALYSIS

A data-cut will be made at the time of preparation of the marketing application to present interim results, Guidance ICH-E1A suggests that at such time, 100 tapinarof subjects should have completed 52 weeks of treatment and 300 tapinarof subjects should have completed 26 weeks of treatment exposure combined over the pivotal studies and the current study. The final analysis will be conducted after study completion (e.g., the last participant's last visit).

10. DATA CONVENTIONS FOR ANALYSIS

10.1 General Statistical Principles

The study efficacy and safety results will be summarized descriptively. There will be no statistical testing.

All observed and derived variables (e.g., change from baseline, percentage change from baseline, and response status) that are summarized will be presented in by-subject listings. Unless otherwise noted, the data will be sorted by DB treatment group and subject number and then by date within subject number.

For categorical parameters, the number and percentage of subjects in each category will be presented. The denominators for percentages will be the number of subjects appropriate for the purpose. For continuous parameters, descriptive statistics will include number of subjects, mean, standard deviation (SD), median, minimum, and maximum.

10.2 Pooling of Study Sites

No by-site summaries are planned.

10.3 Study Day

Day 1 is the date of Visit 1 (which is also the last visit in pivotal studies). Study day is calculated relative to the date of Day 1.

10.4 Baseline and Change from Baseline

For PGA score and % BSA Affected, baseline is defined as the assessment collected at Visit 1 in the extension study. If Visit 1 measurement is missing, the baseline value will be considered as missing.

For all other efficacy and safety assessments (PASI, DLQI, vital signs and laboratory results), baseline is defined as the last available measurement on or after Week 12 visit date in pivotal studies and on or before the Visit 1 visit date in the extension study. If there's no measurement available during this time period, the baseline value will be considered as missing. Change from baseline is the post-baseline value minus baseline unless otherwise specified. Percent change from baseline is $(\text{Change from baseline} / \text{baseline}) * 100\%$.

10.5 Analysis Visit Window

Efficacy and safety endpoints will be summarized according to the nominal visit as assigned by the investigator except for assessments collected on early termination visits. Early termination visit will be re-numbered to the last nominal visit number + 1. For example, if a subject attended Visit 1, Visit 2 (Week 4), Visit 3 (Week 8) and then early terminated, the early termination visit will be re-numbered and analyzed as Visit 4 (Week 12).

Unscheduled visits will not be re-numbered and will not be included in table summaries. They will only be listed.

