- ^j Study diary should only be dispensed if study product is dispensed.
- ^k Subjects will be monitored for disease worsening (PGA ≥ 2), and study drug administration may be started at any time during the observation period (see Section **5.1.5.1**)
- ^l Subjects will be instructed to apply study drug once daily at the approximate same time each day, based on subject preference. This should only occur for subjects receiving study treatment.
- ^m Study drug will be applied after safety assessments have been conducted, . Subjects will be instructed and reminded on how to apply study drug at each visit, except during the final treatment visit (see Section **5.1.5.3** for additional details on timing of study drug application during study visits). This should only occur for subjects receiving study treatment.

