5.1.5.2. Disease Worsening (Physician Global Assessment Score ≥ 2) During the Study

If disease worsening is suspected between scheduled study visits, an unscheduled visit may be performed.

- If disease worsening (ie, PGA ≥ 2) is not confirmed, the subject will continue to be assessed at routine, scheduled visits (see Table 1).
- For each confirmed episode of disease worsening (ie, PGA ≥ 2) during the study (at either a scheduled or unscheduled visit), a treatment course of tapinarof cream (once daily) will be initiated and will continue until the subject achieves a PGA 0, as assessed at scheduled visits, approximately every 4 weeks (see Table 1).
- Subjects subsequently achieving a PGA of 0 will stop study drug and will then be assessed at routine, scheduled visits (see
- Table 1). Subjects who then experience suspected disease worsening between scheduled study visits may contact the study site to arrange an unscheduled visit (see
- Table 1).
 - If disease worsening is not confirmed, the subject will continue to be assessed at routine, scheduled visits.
 - If disease worsening is confirmed (ie, PGA ≥ 2) at either an unscheduled or a scheduled visit, subjects will initiate another treatment course of tapinarof cream (once daily) until a PGA 0 is achieved as described above.
- This treatment and re-treatment pattern of use will be continued until the end of the study (ie, subjects may receive study treatment up until the Week 40 visit).

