7.6. Unscheduled Visits

Unscheduled visits may occur, as needed. For subjects who experience suspected disease worsening (PGA ≥ 2) between scheduled study visits may contact the study site to arrange an unscheduled visit (see Section 5.1.5.2). The following assessments will be performed:

- Brief physical exam
- Vital signs measurements
- Urine pregnancy test (females of CBP), as needed
- Blood sample collection for clinical laboratory tests (serum chemistry, hematology, diagnostic tests), as needed
- Urinalysis, as needed
- Photography of a representative area of the subject's disease area (optional for subjects; at a subset of study centers)
- PGA score
- BSA affected calculation
- PASI
- LTS (if patient has been applying study drug for the treatment period prior to the scheduled visit)
- AE recording
- Concomitant medication recording
- Collect and dispense diary, if applicable (subjects will be instructed in how and when to complete diary)
- Review subject diaries for treatment compliance, if applicable
- Collect and dispense study drug (if applicable)
- Instruction on how to administer study drug (if applicable)
- Study drug administration under supervision (if applicable)

If disease worsening is confirmed, a new treatment course will be initiated.

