11.7 Efficacy Endpoints

Efficacy endpoints are as follows:

For subjects entering the study with a PGA score of clear (0):

- Proportion of subjects who experience PGA ≥ 2 at least 1 time during the study.
- Proportion of subjects who never experience PGA ≥ 2 throughout the study.
- Time to first worsening (PGA ≥ 2), defined as days from date of Visit 1 date to the date of first occurrence of PGA ≥ 2 . Subjects who never experience PGA ≥ 2 throughout the study will be censored at the date of their last PGA assessment.

For subjects entering the study with a PGA score ≥ 1 :

- Proportions of subjects who achieve PGA = 0 at least 1 time during the study

• [REDACTED]

• [REDACTED]

[REDACTED]

For subjects entering the study with a PGA score ≥ 2 :

- Proportions of subjects who achieved PGA = 0 or 1 at least 1 time during the study.
- Proportions of subjects who never achieve PGA = 0 or 1 throughout the study.

The following endpoints will be summarized over subjects in ITT population:

- Duration (days) of treatment episodes, defined as time (days) from the date of each PGA ≥ 2 (or PGA ≥ 1 for the first episode) to 1 day before each subsequent treatment success (PGA = 0). The date of the last PGA assessment will be used as the end date for episodes ongoing at the end of the study.

- [REDACTED]
- [REDACTED] \geq [REDACTED]
- [REDACTED]
- [REDACTED]
- [REDACTED]
- [REDACTED] change and percent change from baseline in %BSA affected by visit (OC and LOCF).
- [REDACTED] change and percent change from baseline in PASI score by visit (OC and LOCF)
- [REDACTED] \geq [REDACTED]
- [REDACTED] \geq [REDACTED]
- [REDACTED] \geq [REDACTED]

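### SAP 10.5 keeps unscheduled visits out of table summaries with no exception; applied literally, it misdates or loses worsenings (PGA ≥ 2) confirmed at unscheduled visits

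*SAP*

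**What the plan says.** SAP 10.5 (Analysis Visit Window) opens by saying that efficacy and safety endpoints are summarized by nominal visit, with early termination visits as the only exception. It then says: "Unscheduled visits will not be re-numbered and will not be included in table summaries. They will only be listed".

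SAP 11.7 defines the PGA endpoints by date or occurrence and names no visit type:
- Time to first worsening, for subjects entering at PGA 0, is "defined as days from date of Visit 1 date to the date of first occurrence of PGA" ≥ 2. Subjects with no such event "will be censored at the date of their last PGA assessment".
- The never-worsened endpoint is "Proportion of subjects who never experience PGA" ≥ 2 throughout the study.
- "Duration (days) of treatment episodes, defined as time (days) from the date of each PGA" ≥ 2 (≥ 1 for the first episode) to the day before the next PGA of 0.

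SAP 11.4 takes expected days exposed and within-episode doses from these same episodes.

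The protocol makes the unscheduled visit a planned route to a worsening. Section 5.1.5.2 says that for each confirmed worsening, "at either a scheduled or unscheduled visit), a treatment course of tapinarof cream (once daily) will be initiated". Section 7.6 lists PGA among the assessments at such visits and adds: "If disease worsening is confirmed, a new treatment course will be initiated". Footnote k of Table 1 says that "study drug administration may be started at any time during the observation period".

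**The concern.** Durability off treatment is one of the main things this extension describes. A subject who flares between visits is invited to come in, is scored, and restarts drug if PGA is 2 or more. Because treatment then begins, PGA may be below 2 at the next scheduled visit, so the unscheduled score can be the only record of that worsening. A rule that sends unscheduled scores to listings alone would remove some real worsenings from the tables and date others late. For the proportion worsened, the error runs one way, towards better durability. Two programmers working from the same SAP could report different results, including at the data-cut planned for the marketing application.

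**Working it through.** The plan states no figure to reproduce: sample size follows the ICH E1 exposure guideline and SAP 10.1 rules out testing. The check is a comparison of the texts, followed by arithmetic on visit dates.

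**1. Is an exception stated?** None in the readable text of SAP 10.5, 11.7, 11.8 or 12. SAP 11.8 says Kaplan-Meier summaries use observed cases, a term that SAP 8 introduces for summaries by visit. That does not settle which visits enter.

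**2. Dating delay.** Inputs: visits every 4 weeks, ±3 days (protocol 3.1). With a gap of g days between scheduled visits and an unscheduled visit k days into it, delay = g − k if PGA is still ≥ 2 at the next scheduled visit.
- Nominal gap, g = 28: 1 to 27 days.
- Widest gap within windows, g = 28 + 3 + 3 = 34: at most 33 days.
- One scheduled visit missed, nominal g = 56: up to 55 days.

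If PGA is below 2 at the next visit but reaches 2 at a later one, the event takes that later date.

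**3. Worked subject (invented).** Enters at PGA 0; unscheduled visit on Day 43 with PGA 2, drug restarted; PGA 0 at Week 12 (Day 85). With all visits used, worsening is on Day 43 and the episode runs Day 43 to Day 84, 84 − 43 + 1 = 42 days.
- (A) PGA ≥ 2 at Week 8 (Day 57). Scheduled visits only: worsening on Day 57, 57 − 43 = 14 days late; episode 84 − 57 + 1 = 28 days, 14/42 = 33% shorter.
- (B) PGA 1 at Week 8 and never ≥ 2 at a later scheduled visit. Scheduled visits only: tabulated as never worsened and censored at the last scheduled PGA, although re-treated for a confirmed worsening. The 42-day episode disappears. This takes the PGA ≥ 1 start in SAP 11.7 to apply to subjects who enter at PGA ≥ 1. If it were applied here, an episode of 28 days would open at Week 8, still short of 42.

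**4. Proportion ever worsened.** Let P be the true proportion, u the share of worsened subjects whose first worsening is seen at an unscheduled visit, and m the share of those with no PGA ≥ 2 at any later scheduled visit. Loss = P × u × m. The documents give none of the three, so every value below is an assumption (loss in percentage points):

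| P | u 10%, m 10% | u 25%, m 25% | u 40%, m 50% |
|---|---|---|---|
| 40% | 0.4 | 2.5 | 8.0 |
| 58% | 0.6 | 3.6 | 11.6 |
| 75% | 0.8 | 4.7 | 15.0 |

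If u or m is zero, the loss is zero.

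**5. Kaplan-Meier median.** Each subject's event moves later or vanishes, but a vanished event becomes a censoring at an earlier scheduled visit, which shrinks the risk set. A constructed case with five subjects: two have PGA 0 at Week 4 (Day 26), unscheduled PGA 2 on Day 43, then are lost; two have PGA 2 at Week 4 (Day 32); one never worsens.
- All visits: S(32) = 3/5 = 0.6; S(43) = 0.6 × 1/3 = 0.2; median Day 43.
- Scheduled only: two censored on Day 26; S(32) = 1/3; median Day 32.

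The median shortened. The case is unusual, but it shows that lengthening is typical rather than certain.

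**6. Exposure.** Later or missing episode starts reduce expected days exposed and within-episode doses in SAP 11.4. Percent compliance is a ratio over the same episodes, so it does not change if adherence is constant.

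**The case against.** The strongest reply is that 10.5 was never meant to reach these endpoints. Its heading and first sentence concern assignment to nominal visits, and the disputed sentence begins with renumbering. Days to first PGA ≥ 2 has no nominal visit to be assigned to, and a specific endpoint definition would normally override a general data convention. Read without limit, 10.5 could also keep adverse events recorded at unscheduled visits out of tables, yet SAP 11.11.1 counts all reported events apart from those resolved before Visit 1. All this makes a by-visit-only reading plausible. It does not remove the problem: the sentence carries no limit and no readable passage supplies one.

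Three stronger readings are tempting and should not be drawn:
- A reader might infer that worsenings will be dropped and durability overstated. The documents do not show which reading will be programmed. Parts of 11.7 are blacked out and the Section 15 outline has no content in the public copy, so an exception there cannot be excluded.
- A reader might infer that time to worsening must lengthen. That holds for each subject's recorded date but not for the Kaplan-Meier estimate (step 5).
- A reader might treat a gap between within-episode and whole-study dose totals as evidence of this error. SAP 11.4 makes them differ by design: the whole-study total adds in-clinic dosing and ignores PGA status.

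It is also fair that the study is descriptive and that unscheduled scores remain visible in listings.

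**Conclusion.** Wrong as written, conditional on the literal reading. SAP 10.5 conflicts with the date- and occurrence-based endpoints of 11.7 and with protocol 5.1.5.2 and 7.6. Under the by-visit-only reading the effect is zero. Under the literal reading three things follow from the documents: the dating delays in step 2, a crude proportion worsened that cannot rise, and episode starts and expected days exposed that can be understated. How many subjects are affected does not follow, so the percentages in step 4 are illustrations only. I put no figure on the Kaplan-Meier shift, which depends on worsening times, dropout and repeat worsening, none of which the documents give. Severity is minor to moderate, since nothing is tested.

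**What to change.** - In SAP 10.5, limit the exclusion to summaries by nominal visit (observed cases and LOCF).
- In SAP 11.7 and 11.8, state that PGA ≥ 2 at any dated assessment, scheduled or unscheduled, counts for the ever/never-worsened and time-to-worsening endpoints and for treatment-episode starts.
- State how a PGA of 0 recorded at an unscheduled visit is handled for episode ends. Protocol 5.1.5.2 ties achieving PGA 0 to scheduled visits, so the SAP rule and that passage must be reconciled; using every unscheduled score to end episodes is not automatically right.
- Report the number and percent of worsenings first seen at unscheduled visits, overall and by double-blind treatment group.

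The cost is a few sentences and a little programming, since the scores and dates are already collected and listed. The downside is that durability figures may look slightly less favourable than under the literal rule. If the narrow reading was always intended, the clarification of 10.5 changes no result.

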2. OBJECTIVES AND ENDPOINTS

The objectives and associated endpoints of this study are as follows:

Objectives	Associated Endpoints

 To evaluate the safety and tolerability of tapinarof cream, 1% in adults with plaque psoriasis 	
 Incidence, frequency, and nature of AEs and SAEs Change over time in clinical laboratory tests and frequency of clinically significant abnormal test results Change over time in vital signs and frequency of clinically significant abnormal results [REDACTED]

 To describe the efficacy of tapinarof cream, 1% over an extended period of time in adults with plaque psoriasis 	
 Proportion of subjects who experience a PGA ≥ 2 at least 1 time in the study and the median time from baseline to first worsening (PGA ≥ 2) for subjects entering the study with a PGA score of clear (0) Proportion of subjects who achieve a PGA score of 0 at least 1 time in the study [REDACTED] Duration of each treatment episode, defined as time from each treatment initiation/re-initiation to each subsequent treatment success (PGA score of 0). [REDACTED] Proportion of subjects who never achieve a PGA ≥ 2 throughout the study Proportion of subjects who never achieve a PGA score of 0 or 1 throughout the study [REDACTED] [REDACTED] Change and percent change from baseline in %BSA affected by visit (OC and LOCF) Change and percent change in PASI score by visit (OC and LOCF) [REDACTED]

 To describe the effect of tapinarof cream, 1% on psoriasis symptom severity and the associated impact on daily activities and attitudes in adults with plaque psoriasis 	
 Change in disease impact on daily activities, as measured by the Dermatology Life Quality Index (DLQI) total and individual dimension scores

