6.3.4. Clinical Safety Laboratory Assessments

All protocol-required laboratory assessments must be conducted in accordance with the Study Reference Manual or Laboratory Manual, and Protocol Schedule of Assessments. Laboratory requisition forms must be completed, and samples must be clearly labeled with the Subject number, protocol number, site/center number, and visit date. Details for the preparation and shipment of samples will be provided by the laboratory and are detailed in the Study Reference Manual or the Laboratory Manual. Reference ranges for all safety parameters will be provided to the site by the laboratory responsible for the assessments.

A list of clinical laboratory tests and parameters is provided in [Table 3](#).

All laboratory tests with values that are considered clinically significantly abnormal during participation in the study should be repeated until the values return to normal or baseline. If such values do not return to normal within a period judged reasonable by the Investigator, the etiology should be identified, if possible, and the Sponsor notified.

Table 3: Laboratory Tests

Diagnostic Screening Tests		
• HBsAg	• Pregnancy tests: (urine; women of CBP only)	• Anti-HBc
Serum Chemistry		
• BUN	• Total carbon dioxide	• Uric acid
• Creatinine	• Calcium	• Total bilirubin
• Glucose (fasting not required)	• AST	(+fractionated if required)
• Sodium	• ALT	• Total protein
• Potassium	• Alkaline phosphatase	• Albumin
• Chloride		
Hematology		
• Platelet count	• RBC Indices:	• WBC Differential:
• RBC count	MCV	Neutrophils
• WBC count (absolute)	MCH	Lymphocytes
• Reticulocyte count	MCHC	Monocytes
• Hemoglobin	Reticulocyte percentage	Eosinophils
• Hematocrit		Basophils
Urinalysis		
• Specific gravity	• Dipstick:	
• Microscopic examination (if blood or protein is abnormal)	pH, glucose, protein, blood ketones	

ALT = alanine aminotransferase; Anti-HBc = anti-hepatitis B core antigen; AST = aspartate aminotransferase; BUN = blood urea nitrogen; CBP = child-bearing potential; FSH = follicle stimulating hormone; GGT = gamma-glutamyltransferase; HBsAg = hepatitis B surface antigen; MCH = mean corpuscular hemoglobin; MCHC = mean corpuscular hemoglobin concentration; MCV = mean corpuscular volume; RBC = red blood cell(s); WBC = white blood cell(s).

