8.1.3. Adverse Events of Special Interest

In prior clinical studies, the following AEs have been identified as AEs of particular clinical importance and will be reported as AESIs in this study; in each case, study drug may be discontinued, and study drug may be restarted when event resolves:

- Contact dermatitis: the study site should collect location, duration, size, associated symptoms (itching, burning, pain), severity (mild, moderate, severe), and photograph the affected site (if possible). If the subject contacts the study site to report significant skin irritation at or near the site of study drug application between study visits, the subject should be brought for an unscheduled visit, if possible.
- Folliculitis: the study site should collect the location, duration, size, associated symptoms (itching, burning, pain), severity (mild, moderate, severe), indicate whether pustular, and photograph the affected site (if possible)
- Headache: the study site should collect duration, severity (mild, moderate, severe), onset, and location

Additional AESIs may be identified by the Drug Safety Physician and if applicable by the Clinical Study Team Physician during the evaluation of safety data for the Clinical Study Report. For each AESI, a narrative may be written and included in the Clinical Study Report.

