11.11.4 Vital Signs

Observed values and change from baseline in vital sign parameters (systolic and diastolic blood pressure [SBP, DBP], pulse rate, and body temperature) will be summarized descriptively by visit, overall and by DB treatment group. Vital sign values will be classified as normal, low, high, based on reference ranges as per Table below. Subjects with markedly abnormal changes will be flagged in listing and tabulated separately.

	Absolute Values			Change (Absolute) from Baseline	
	Low	Normal	High	Abnormal Change	Markedly Abnormal Change
SBP	<90 mmHg	90-140 mmHg	>140 mmHg	≥ 20 mmHg	≥ 40 mmHg
DBP	<50 mmHg	50-90 mmHg	>90 mmHg	≥ 10 mmHg	≥ 20 mmHg
Pulse	<50 bpm	50-100 bpm	>100 bpm	≥ 10 bpm	≥ 30 bpm

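### SAP 10.5 keeps unscheduled-visit values out of every table, so peak local-tolerability scores, off-schedule laboratory shifts and marked vital-sign changes can go uncounted

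*SAP*

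**What the plan says.** SAP 10.5 sets the rule for both kinds of endpoint: "Efficacy and safety endpoints will be summarized according to the nominal visit as assigned by the investigator". Early termination visits are renumbered to the next nominal visit. For unscheduled visits it says "Unscheduled visits will not be re-numbered and will not be included in table summaries", and then "They will only be listed".

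The safety sections that follow do not relax this:

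- **SAP 11.11.2 (LTS):** scores are summarised by visit.
- **SAP 11.11.3 (laboratory):** values are summarised by visit, with shift tables for abnormality status. Markedly abnormal values go to listings.
- **SAP 11.11.4 (vital signs):** values are summarised by visit. In addition, "Subjects with markedly abnormal changes will be flagged in listing and tabulated separately".

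On the protocol side, section 8.1.3 says, under contact dermatitis, that if a subject reports significant irritation at or near the application site between visits, "the subject should be brought for an unscheduled visit, if possible". Section 7.6 lists what is done at an unscheduled visit: vital signs, LTS if the subject has been applying drug, and laboratory tests as needed. Section 6.3.4 says that clinically significantly abnormal laboratory tests "should be repeated until the values return to normal or baseline". The safety endpoints in section 2 include "frequency of clinically significant abnormal test results" and a matching item for vital signs. Neither is limited to scheduled visits.

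**The concern.** Safety and tolerability is the first-listed objective. The protocol creates a route by which a subject with troublesome irritation is seen, and scored, outside the visit schedule. The SAP then keeps that score out of every table. LTS is tabulated only by visit, so no other LTS table could pick it up. A reader of the tables could not tell how many subjects ever reached an LTS score of 3 or 4.

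The same rule affects two other sets of tables: the laboratory shift tables, where scheduled draws are sparse, and the tabulation of markedly abnormal vital-sign changes, where SAP 11.11.4 suggests a per-subject count that 10.5 would restrict without saying so.

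**Working it through.** The plan gives no figure to reproduce and plans no statistical testing. The check sets the sections side by side and adds a small illustration.

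**1. LTS**

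- Irritation reported between visits leads to an unscheduled visit, if possible (protocol 8.1.3).
- LTS is scored there if the subject was applying drug (7.6). Irritation at or near the application site will normally meet that condition.
- Drug may be interrupted for skin irritation (1.3.1.1, 4.6.2, 8.1.3).
- Table 1, footnote i, requires LTS only if drug was being applied in the period before the visit. After an interruption, the next scheduled visit may have no LTS score, or one taken after the reaction has settled.
- The unscheduled score is listed only (SAP 10.5), and the LTS table is by visit (SAP 11.11.2).

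The peak score can therefore be absent from the LTS tables.

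**2. Laboratory values**

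- Among Visits 2 to 10, blood is drawn at Weeks 4 and 12 only (protocol 7.2). The next draw is at Week 40 (7.3), then follow-up (7.4), or at early termination (7.7).
- Gap: 40 − 12 = 28 weeks.
- Within that gap, any value not drawn at an early termination visit is unscheduled and enters neither the by-visit summary nor the shift table.

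**3. Vital signs**

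- These are measured at every scheduled visit and at unscheduled visits (7.2, 7.6), so the gap is smaller.
- SAP 11.11.4 tabulates subjects with markedly abnormal changes (systolic at least 40 mmHg, diastolic at least 20 mmHg, pulse at least 30 bpm) and does not limit the count to scheduled visits. SAP 10.5 excludes unscheduled visits from table summaries. The two sections need reconciling.

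**4. What still reaches a table**

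- Investigator-judged clinically significant laboratory or vital-sign abnormalities, and symptomatic application-site complaints, are adverse events (protocol 8.1.1).
- Adverse event tables do not depend on visit type. They include maximum grade and, for contact dermatitis, folliculitis and headache, the most extreme level of each characteristic (SAP 11.11.1).

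**5. Illustration of size (assumptions, not document figures)**

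Suppose an irritation episode lasts d days, is shorter than the visit gap, and starts at a uniformly random time. The chance that it falls wholly between two scheduled visits is 1 − d/gap. Visits are 28 days apart. Moving one of two adjacent visits by the permitted 3 days gives gaps of 25 to 31 days.

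| d (days) | gap 28 | gap 25 to 31 |
|---|---|---|
| 7 | 1 − 7/28 = 75% | 72% to 77% |
| 14 | 1 − 14/28 = 50% | 44% to 55% |
| 21 | 1 − 21/28 = 25% | 16% to 32% |

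Now let u be the share of the planned 850 subjects with an on-drug unscheduled visit, and w the share of those whose worst LTS score falls there. The number affected is 850 × u × w:

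- u = 2%, w = 25%: 850 × 0.02 × 0.25 = 4.25, about 4 subjects.
- u = 20%, w = 75%: 850 × 0.20 × 0.75 = 127.5, about 128 subjects.

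The documents give neither u, w nor the duration of episodes. The width of this range shows that the size cannot be determined from the plan.

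**The case against.** The strongest reply is that the adverse event tables already do this work. They take in contact dermatitis, application-site complaints and clinically significant abnormal results whatever the visit, and the special-interest summary is itself a worst-case table. The study is descriptive and every value is listed. Most of this stands, and it confines the point to three sets of tables. It does not remove the point, because an adverse event grade is not an LTS score. A laboratory or vital-sign abnormality becomes an adverse event only on the investigator's judgement, whereas the shift tables use laboratory ranges and SAP 11.11.4 uses fixed thresholds.

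A reader might infer four stronger claims that the documents do not support:

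- **That subjects with abnormal laboratory or vital-sign results are sent to unscheduled visits.** Protocol 6.3.4 asks only for repeat tests, and nothing comparable is said for vital signs. A repeat follows the abnormal value; if that value came from a scheduled visit, it is already tabulated.
- **That the safety tables as a whole leave out the worst values, or that clinically significant results are necessarily undercounted.** Such results are adverse events under protocol 8.1.1 and reach those tables.
- **That unscheduled visits are mainly safety visits.** The reason the protocol gives repeatedly is suspected disease worsening (5.1.5.1, 5.1.5.2, 7.6), often when the subject is off drug and LTS is not required.
- **That the by-visit LTS summary is biased because it omits off-schedule readings.** Protocol 10.4.3 asks for a by-visit LTS summary, and adding symptom-triggered readings to a nominal week would over-represent symptomatic subjects. What is missing is a separate any-time summary.

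One further limit applies. The table outline in SAP section 15 has no content in the available text, so the absence of a worst-value row can be stated only for the SAP's prose.

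**Conclusion.** The point holds in a limited form. As written, the SAP can leave peak LTS scores, off-schedule laboratory shifts and markedly abnormal vital-sign changes uncounted in the tables meant to show them. LTS is the clearest case, because the protocol itself directs irritated subjects to a visit whose scores are not tabulated and may not be repeated. For laboratory data, the exposed period is the 28 weeks between the Week 12 and Week 40 draws, early termination visits aside. For vital signs, the problem rests on a literal reading of 10.5 against 11.11.4.

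The number of subjects affected is unknown, and the range of about 4 to 128 rests wholly on assumed rates. The consequence is incomplete description of part of the first objective. It does not mean that significant events are lost from the report. The change is worth making because the data are already collected.

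**What to change.** Keep by-visit summaries on nominal visits and make these changes to the SAP:

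1. **Section 10.5:** limit the exclusion, for example: *Unscheduled visits are excluded from by-visit summaries only. They contribute to any-time and worst post-baseline summaries.*
2. **Section 11.11.2 (lead case):** add, for the investigator and the subject scale separately, the number and percentage of subjects by highest post-baseline LTS score, using all scheduled, unscheduled and early termination assessments.
3. **Section 11.11.3:** add a shift from baseline to the worst post-baseline category from the same assessments, with low and high directions shown separately.
4. **Section 11.11.4:** state that the abnormal and markedly abnormal change categories use the worst post-baseline value from the same assessments.

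The denominator for each should be subjects with at least one post-baseline assessment of that measure.

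The cost is SAP wording and a few extra table rows, with no new data collection. Abnormality counts will look slightly less favourable. Subjects assessed more often have more chances to record a high value, so the new rows should be labelled as any-time results and not read against the by-visit percentages.
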